3.1. ASSESSMENT OF SEVERITY

The Investigator will make an assessment of severity for each AE and SAE reported during the study and assign it to one of the categories provided in [Table 1](#) (as a guidance for assessing adverse event severity).

The terms “severe” and “serious” are not synonymous. Severity refers to the intensity of an adverse event (rated as mild, moderate, or severe, or according to a pre-defined grading criteria [e.g., National Cancer Institute Common Terminology Criteria for Adverse Events [NCI CTCAE] criteria); the event itself may be of relatively minor medical significance (such as severe headache without any further findings).

Severity and seriousness need to be independently assessed for each adverse event recorded on the eCRF.

Serious adverse events are required to be reported by the Investigator to the Sponsor immediately (i.e., no more than 24 hours after learning of the event).

The adverse event severity grading scale for the NCI CTCAE (v5.0) will be used for assessing adverse event severity. [Table 1](#) will be used for assessing severity for adverse events that are not specifically listed in the NCI CTCAE.

Table 1 Adverse Event Severity Grading Scale

Grade	Severity
1	Mild; asymptomatic or mild symptoms; clinical or diagnostic observations only; or intervention not indicated
2	Moderate; minimal, local, or non-invasive intervention indicated; or limiting age-appropriate instrumental activities of daily living ^a
3	Severe or medically significant, but not immediately life-threatening; hospitalization or prolongation of hospitalization indicated; disabling; or limiting self-care activities of daily living ^{b,c}
4	Life-threatening consequences or urgent intervention indicated ^d
5	Death related to adverse event ^d

NCI CTCAE = National Cancer Institute Common Terminology Criteria for Adverse Events.

Note: Based on the NCI CTCAE (v5.0), which can be found at:

https://ctep.cancer.gov/protocolDevelopment/electronic_applications/docs/CTCAE_v5_Quick_Reference_8.5x11.pdf

- ^a Instrumental activities of daily living refer to preparing meals, shopping for groceries or clothes, using the telephone, managing money, etc.
- ^b Examples of self-care activities of daily living include bathing, dressing and undressing, feeding one's self, using the toilet, and taking medications, as performed by patients who are not bedridden.
- ^c If an event is assessed as a "significant medical event," it must be reported as a serious adverse event (see Section 6 of this Appendix for reporting instructions), per the definition of serious adverse event in Section 2.
- ^d Grade 4 and 5 events must be reported as serious adverse events (see Section 6 for reporting instructions), per the definition of serious adverse event in Section 2.

3.2. ASSESSMENT OF CAUSALITY

Investigators should use their knowledge of the participant, the circumstances surrounding the event, and an evaluation of any potential alternative causes to determine whether or not an adverse event is considered to be related to the study treatment, indicating "yes" or "no" accordingly. The following guidance should be taken into consideration:

- Temporal relationship of event onset to the initiation of study treatment.
- Course of the event, considering especially the effects of dose-reduction, discontinuation of study treatment.
- Known association of the event with the study treatment or with similar treatments.
- Known association of the event with the disease under study.
- Presence of risk factors in the participant or use of concomitant medications known to increase the occurrence of the event.
- Presence of non-treatment-related factors that are known to be associated with the occurrence of the event.

For participants receiving combination therapy, causality will be assessed individually for each protocol-mandated therapy.

4. FOLLOW-UP OF AES AND SAES

The Investigator is obligated to perform or arrange for the conduct of supplemental measurements and/or evaluations as medically indicated or as requested by the Sponsor's Medical Monitor to elucidate the nature and/or causality of the AE or SAE as fully as possible. This may include additional laboratory tests or investigations, histopathological examinations, or consultation with other health care professionals.

New or updated information will be recorded in the originally completed eCRF.

The Investigator will submit any updated SAE data to the Sponsor within 24 hours of receipt of the information.

5. IMMEDIATE REPORTING REQUIREMENTS FROM INVESTIGATOR TO SPONSOR

Certain events require immediate reporting to allow the Sponsor to take appropriate measures to address potential new risks in a clinical trial. The Investigator must report such events to the Sponsor immediately; under no circumstances should reporting take place more than 24 hours after the Investigator learns of the event. The following is a list of events that the Investigator must report to the Sponsor within 24 hours after learning of the event, regardless of relationship to study treatment:

- Serious adverse events
- Non-serious adverse events of special interest (NSAESI)
- Pregnancies (see Section [8.3.5](#))

The Investigator must report new significant follow-up information for these events to the Sponsor immediately (i.e., no more than 24 hours after becoming aware of the information). New significant information includes the following:

- New signs or symptoms or a change in the diagnosis.
- Significant new diagnostic test results.
- Change in causality based on new information.
- Change in the event's outcome, including recovery.
- Additional narrative information on the clinical course of the event.

Investigators must also comply with local requirements for reporting serious adverse events to the local Health Authority and IRB/EC.

5.1 REPORTING REQUIREMENTS OF SERIOUS ADVERSE EVENTS AND NON-SERIOUS ADVERSE EVENTS OF SPECIAL INTEREST

Events that Occur prior to Study Treatment Initiation

After informed consent has been obtained but prior to initiation of study treatment, only serious adverse events caused by a protocol-mandated intervention should be reported. The Serious Adverse Event/Adverse Event of Special Interest Reporting Form provided to Investigators should be completed and submitted to the Serious Adverse Event Responsible immediately (i.e., no more than 24 hours after learning of the event).

Events that Occur after Study Treatment Initiation

For reports of serious adverse events and non-serious adverse events of special interest (Section 8.3.6) that occur after initiation of study treatment (Section 8.3.1), investigators should record all case details that can be gathered immediately (i.e., within 24 hours after learning of the event) on the appropriate Adverse Event of Special Interest/ Serious Adverse Event eCRF form and submit the report via the electronic data capture (EDC) system. A report will be generated and sent to the Sponsor's Safety Risk Management department.

In the event that the EDC system is unavailable, the Serious Adverse Event/Adverse Event of Special Interest Reporting Form provided to investigators should be completed and submitted to the Serious Adverse Event Responsible immediately (i.e., no more than 24 hours after learning of the event).

Once the EDC system is available, all information will need to be entered and submitted via the EDC system.

Reporting of Post-Study Adverse Events and Serious Adverse Events

If the Investigator becomes aware of any other serious adverse event occurring after the end of the AE reporting period, if the event is believed to be related to prior study treatment the event should be reported directly to the Sponsor or its designee, either by faxing or by scanning and emailing the SAE Reporting Form using the fax number or email address provided to investigators.

5.2 REPORTING REQUIREMENTS FOR CASES OF ACCIDENTAL OVERDOSE OR MEDICATION ERROR

Accidental overdose and medication error (hereafter collectively referred to as "special situations"), are defined as follows:

- Accidental overdose: accidental administration of a drug in a quantity that is higher than the assigned dose
- Medication error: accidental deviation in the administration of a drug
In some cases, a medication error may be intercepted prior to administration of the drug.

Special situations are not in themselves adverse events, but may result in adverse events. Each adverse event associated with a special situation should be recorded separately on the Adverse Event eCRF. If the associated adverse event fulfills seriousness criteria, the event should be reported to the Sponsor immediately (i.e., no more than 24 hours after learning of the event). For RO7239958 or placebo, adverse events associated with special situations should be recorded as described below for each situation:

- Accidental overdose: Enter the drug name and "accidental overdose" as the event term. Check the "Accidental overdose" and "Medication error" boxes.
- Medication error that does not qualify as an overdose: Enter the adverse event term. Check the "Medication error" box.
- Medication error that qualifies as an overdose: Enter the adverse event term. Check the "Accidental overdose" and "Medication error" boxes.

In addition, all special situations associated with RO7239958 or placebo, regardless of whether they result in an adverse event, should be recorded on the Adverse Event eCRF and reported to the Sponsor immediately (i.e., no more than 24 hours after learning of the event; see [Appendix 2](#), Section 5.1). Special situations should be recorded as described below:

- Accidental overdose: Enter the drug name and "accidental overdose" as the event term. Check the "Accidental overdose" and "Medication error" boxes.
- Medication error that does not qualify as an overdose: Enter the name of the drug administered and a description of the error (e.g., wrong dose administered, wrong dosing schedule, incorrect route of administration, wrong drug, expired drug administered) as the event term. Check the "Medication error" box.
- Medication error that qualifies as an overdose: Enter the drug name and "accidental overdose" as the event term. Check the "Accidental overdose" and "Medication error" boxes. Enter a description of the error in the additional case details.
- Intercepted medication error: Enter the drug name and "intercepted medication error" as the event term. Check the "Medication error" box. Enter a description of the error in the additional case details.

As an example, an accidental overdose that resulted in a headache would require the completion of two Adverse Event eCRF pages, one to report the accidental overdose and one to report the headache. The "Accidental overdose" and "Medication error" boxes would need to be checked on both eCRF pages.

6. EXPEDITED REPORTING TO HEALTH AUTHORITIES, INVESTIGATORS, INSTITUTIONAL REVIEW BOARDS, AND ETHICS COMMITTEES

The Sponsor will promptly evaluate all serious adverse events and NSAESI against cumulative product experience to identify and expeditiously communicate possible new safety findings to investigators, IRBs, ECs, and applicable Health Authorities based on applicable legislation.

To determine reporting requirements for single adverse event cases, the Sponsor will assess the expectedness of these events using the following reference document{s):

- RO7239958 Investigator's Brochure

The Sponsor will compare the severity of each event and the cumulative event frequency reported for the study with the severity and frequency reported in the applicable reference document.

Reporting requirements will also be based on the Investigator's assessment of causality and seriousness, with allowance for upgrading by the Sponsor as needed.

Certain adverse events are anticipated to occur in the study population at some frequency independent of study treatment exposure and will be excluded from expedited reporting. These anticipated events include, but are not limited to, the following:

- Isolated ALT/AST elevation < 5x ULN (with normal liver function tests) in healthy participants
- Isolated ALT/AST elevation < 8x baseline (with normal liver function tests) in CHB patients

Appendix 3

Procedures for Recording Adverse Events

Investigators should use correct medical terminology/concepts when recording adverse events on the Adverse Event eCRF. Avoid colloquialisms and abbreviations.

Only one adverse event term should be recorded in the event field on the Adverse Event eCRF.

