3. OBJECTIVES AND ENDPOINTS

The objectives and corresponding endpoints are provided in [Table 7](#).

Table 7 Objectives and Endpoints

	Objectives	Endpoints
Primary		
All parts	Safety 
 To assess the safety and tolerability of RO7239958 compared to placebo after single subcutaneous (SC) ascending doses in healthy participants and multiple SC ascending doses in CHB patients stable on NUC therapy. 	
 Incidence, severity, and causal relationship of adverse events (AEs). Changes in vital signs, physical findings and electrocardiogram (ECG) findings, and clinical laboratory results during and following RO7239958 administration. Incidence of injection site reactions (ISRs).
Secondary		
All Parts	Pharmacokinetics (PK) 
 To assess plasma and urine PK of RO7239958 after single ascending SC doses in healthy participants and after multiple SC doses in CHB patients on stable NUC therapy. 	
 Plasma and urine PK parameters determined using non-compartmental analysis (NCA). The following plasma PK parameters will be calculated: 
 Time to maximum concentration (T_{max}). Maximum plasma concentration observed (C_{max}). Area under the curve (AUC) for various time intervals post-dose. Additional PK parameters may be calculated in plasma (e.g., apparent clearance [CL/F], terminal half-life [$t_{1/2}$], K [elimination rate constant]). Additional urine parameters may be calculated, e.g., cumulative amount of drug excreted in urine over defined time periods (A_e).

Table 7 Objectives and Endpoints (cont.)

Part 2a and 2b	Pharmacodynamics (PD) 
 To assess the antiviral activity of RO7239958 after multiple ascending SC doses in CHB patients on stable NUC therapy. 	
 Time course profile of HBsAg levels and maximum decline from baseline. Time course profile of hepatitis B surface antibody (anti-HBs) levels. In participants that are HBeAg positive at study entry, incidence of HBeAg loss and incidence of hepatitis B e antibody (anti-HBe) seroconversion. Participants will have a suppressed HBV DNA at study entry and will be monitored to ensure that HBV DNA suppression is maintained during the study.
Exploratory		

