8.4 TREATMENT OF OVERDOSE

Study treatment overdose is the accidental administration of a drug in a quantity that is higher than the assigned dose. An overdose or incorrect administration of study treatment is not an adverse event unless it results in untoward medical effects (see Sections 5 and 5.2 of [Appendix 2](#) for further details).

In the event of an overdose, the Investigator should:

1. Contact the Sponsor's Medical Monitor immediately.
2. Closely monitor the participant for AE/SAE and laboratory abnormalities until resolved.
3. Document the quantity of the excess dose, as well as the reason and circumstances, and duration of the overdose, in the CRF.

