9.4.2 Safety Analyses

All safety analyses will be based on the entire safety analysis population (see [Table 11](#)).

The objectives of the safety analyses are to assess the safety and tolerability of RO7239958 compared to placebo after single SC ascending doses in healthy participants and multiple SC ascending doses in CHB patients.

Participants randomized to receive RO7239958 will be analyzed by cohort or arm. All study subjects who are randomized to receive placebo will be pooled as respective placebo control groups, according to each part of the study (See Section 9).

The safety data, including AEs, ISRs, reason for withdrawal from study, laboratory data, ECG, concomitant medications, vital signs, and physical examination results will be listed and summarized descriptively. Marked abnormalities of laboratory data will be flagged. As appropriate, listings, summary tables and graphs (participant plot and/or mean plots) will be provided to describe safety and tolerability assessments.

Table 12 Safety Statistical Analysis Methods

Endpoint	Statistical Analysis Methods
Adverse events	The original terms recorded on the eCRF by the Investigator for adverse events will be coded by the Sponsor. Adverse events will be summarized by mapped term and appropriate thesaurus level.
Clinical laboratory tests	All clinical laboratory data will be stored on the database in the units in which these were reported. Laboratory test values will be presented in International System of Units (SI units; Système International d'Unités) by individual listings with flagging of abnormal results. Summary tables of change from baseline over time will be displayed. Shifts in NCI CTCAE grades v5.0 from baseline to the worst grade observed during treatment will be presented for selected laboratory parameters. See Appendix 4 for details on standard reference ranges and data transformation and the definition of laboratory abnormalities.
Vital signs	Vital signs data will be presented by individual listings with flagging of values outside the normal ranges and flagging of abnormalities. In addition, tabular summaries will be used, as appropriate.
ECG data analysis	For the analyses of ECG data, see Section 8.2.3 .
Concomitant medications	The original terms recorded on the participants' eCRF by the Investigator for concomitant medications will be standardized by the Sponsor by assigning preferred terms. Concomitant medications will be presented in summary tables and listings.

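### Appendix 2, Section 5.2: the overdose bullet gives the wrong event term for a resulting adverse event, and Table 12 does not say how special-situation records are handled

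*Combined protocol and SAP*

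**What the plan says.** Appendix 2, Section 5.2 groups accidental overdose and medication error as special situations and gives two lists for recording them on the Adverse Event eCRF.

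- **First list: the adverse event associated with the special situation.** For overdose: "Accidental overdose: Enter the drug name and 'accidental overdose' as the event term". For a medication error, whether or not it amounts to an overdose, the site enters the term of the adverse event.
- **Second list: the special situation itself.** The lead-in says "all special situations associated with RO7239958 or placebo, regardless of whether they result in an adverse event, should be recorded on the Adverse Event eCRF". The overdose wording is the same as in the first list. For an error caught before administration: "Enter the drug name and 'intercepted medication error' as the event term". Errors that are not overdoses get the drug name and a description of the error.

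The section also requires each associated adverse event to be recorded separately. Its example, an overdose followed by a headache, needs two pages, "one to report the accidental overdose and one to report the headache", with both tick boxes checked on both pages.

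On status, Section 5.2 says "Special situations are not in themselves adverse events, but may result in adverse events", and Section 8.4 says "An overdose or incorrect administration of study treatment is not an adverse event unless it results in untoward medical effects".

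On analysis, Table 12 in Section 9.4.2 says "The original terms recorded on the eCRF by the Investigator for adverse events will be coded by the Sponsor" and that adverse events are summarised by mapped term. Section 9 has no sentence on special-situation records. Under Section 3, the incidence, severity and causal relationship of adverse events are a primary endpoint in all parts.

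**The concern.** The first overdose bullet is an operative instruction to sites, and its content fits the second list. It tells the site to put the name of the mistake where the name of the resulting event belongs. The participants affected would be those who received more drug than assigned, whose adverse events a first-in-human study most needs under the right term.

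The secondary matter is one of analysis. The recording rule creates records on the adverse event form that the protocol itself says are not adverse events, and the analysis section does not say what to do with them. Two programmers could reasonably produce different adverse event tables from the same data. The study is descriptive, so these tables are the primary safety result.

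**Working it through.** **1. The recording rule.** Take one participant with an accidental overdose and a headache.

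| Instruction followed | Term for the special situation | Term for the adverse event |
|---|---|---|
| First list, overdose bullet | drug name + accidental overdose | drug name + accidental overdose |
| First list, third bullet (error that is an overdose) | drug name + accidental overdose | headache |
| Worked example | drug name + accidental overdose | headache |

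Section 5.2 defines a medication error as an accidental deviation in giving a drug. An accidental overdose meets that definition, so this case falls under the first and third bullets together, and they give different terms. Appendix 3 allows one term per event field, so a site following the first bullet cannot also enter the headache on that page.

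**2. Group sizes (Section 9.2; placebo pooling from Section 9).** The plan's totals reproduce: 4 to 5 cohorts × 10 = 40 to 50 in Part 1; 4 to 7 arms × 7 = 28 to 49 in Part 2; 4 to 5 × 7 = 28 to 35 in Part 2a; 2 × 7 = 14 in Part 2b.

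**3. Effect of one record.** If a special situation without an adverse event were counted, and the participant had no other adverse event, incidence would rise by 100/n percentage points:

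| Group | n | Shift (points) |
|---|---|---|
| Part 1 active cohort | 8 | 12.5 |
| Part 2 active arm | 6 | 16.7 |
| Part 1 pooled placebo | 8 to 10 | 12.5 to 10.0 |
| Part 2a pooled placebo | 4 to 5 | 25.0 to 20.0 |
| Part 2b pooled placebo | 2 | 50.0 |

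**4. How often.** The documents give no error rate. Assume that a fraction q of participants, from 1% to 10%, has such a record. The chance of at least one among n is 1 − (1 − q)^n:

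- n = 6: 1 − 0.99^6 = 5.9%, up to 1 − 0.90^6 = 46.9%.
- n = 8: 1 − 0.99^8 = 7.7%, up to 1 − 0.90^8 = 57.0%.

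With true adverse event incidence p, independent of q, the expected inflation if the records are counted is (1 − p) × q. Taking p from 30% to 70% as a further assumption, it runs from 0.30 × 1% = 0.3 points to 0.70 × 10% = 7.0 points.

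**5. The tick boxes.** In the example both boxes are checked on the headache page as well as the overdose page. A filter on the boxes would therefore remove the headache. Only the event term separates the two records, and for errors that are not overdoses that term is a free description.

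**6. The two points interact.** If special-situation records are filtered out by event term while the first overdose bullet stands, a headache entered as accidental overdose is filtered out too.

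**The case against.** A reader might infer that Table 12 counts every term on the adverse event form, so that primary incidence is inflated. The text does not support that. Table 12 covers terms recorded for adverse events, and Sections 8.4 and 5.2 say special situations are not adverse events. Read together, they point towards exclusion. What stands is that no sentence says so.

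A reader might also infer that the headache is lost. It is lost only if the site follows one bullet over the separate-recording sentence, the third bullet and the worked example. The bullet looks like a drafting slip, its wording shared with the second list. That limits the harm, but a site should not have to decide which instruction prevails.

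Other mitigating points are fair. Summaries are by mapped term, so an accidental overdose would probably appear as its own term rather than merge into a clinical one. None of the specific stopping criteria in Section 4.1.3 uses overall adverse event incidence. In the headache example the participant has an adverse event in any case, so counting the overdose as well leaves participant-level incidence unchanged, although the event count would rise.

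A separate analysis plan might state the rule, since the abbreviation list includes CSAP. None is among the documents reviewed, and it would not correct an instruction to sites.

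**Conclusion.** The first overdose bullet in Appendix 2, Section 5.2 is wrong as written. It conflicts with the rest of its list, the separate-recording sentence and the section's own example, and it bears on the terms that feed a primary endpoint. It should be corrected.

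The silence of Table 12 is a smaller matter: a missing handling rule, with inflation possible but not shown. The shifts of 12.5 points (n = 8) and 16.7 points (n = 6) rest on three conditions together: a special situation without an adverse event occurs, it is counted despite the protocol's definition, and the participant has no other adverse event. They also use the nominal group sizes. Section 5.5 allows up to two extra patients per Part 2 arm, which would make the shift smaller wherever n grows. The expected inflation of 0.3 to 7.0 points depends wholly on the assumed ranges for q and p.

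**What to change.** 1. In the first list of Appendix 2, Section 5.2, change the overdose bullet so that the site enters the term of the resulting adverse event and checks both the overdose and medication-error boxes. This matches the third bullet and the example. The second list stays as it is.
2. Add to Table 12 that records whose event term is the special situation itself are left out of the adverse event summaries and shown in a separate listing. Identify them by event term, with review of the free-text medication-error terms, and not by the tick boxes.

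Make the first change with or before the second, for the reason in step 6 of the working. The cost is one changed phrase, one added sentence, one listing and a short term review. What sites report to the sponsor, and how quickly, does not change.
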